The study team will phone pre-screen potential participants prior to scheduling an in-person baseline evaluation. The phone pre-screen will assess inclusion and exclusion criteria using a brief telephone interview guide to screen for dementia using the AD-8 assessment and for depression using the PHQ9 assessment, as well as demographics. If it has been more than 60 days (+/- 2 weeks) since the AD-8 and PHQ9 have been completed and the date of the baseline visit, an additional AD-8 and PHQ9 will be done within the prescreening period to ensure there is no more than 60 days between screening with AD-8 and PHQ9 and the baseline visit. Individuals deemed eligible who consent to participate in the study will be placed into 1 of the 3 trial cohorts. Cohort 1 will include 10 people, cohort 2 will include 10 people, and cohort 3 will include 10 people. All participants will be asked to provide informed consent before completing any baseline assessments. Baseline evaluations will include body composition, cardiovascular assessments, dietary assessments, and cognitive assessments.

Baseline evaluation: The baseline evaluation will consist of a 1-day visit to the University of Kansas Alzheimer's Disease Research Center (KU ADRC). Participants will typically be consented in person the day of the baseline evaluation by study staff. In certain circumstances, in which the participant needs a shortened length of time spent at the clinic for the baseline visit, remote consent may be conducted within a few days prior to the baseline visit. Prior to completion of any baseline procedures, study staff will first review the inclusion and exclusion criteria and confirm that the participant meets eligibility.

Participants will then complete the dietary assessments, body composition assessment, cardiometabolic risk assessments, and cognitive assessment at the KU ADRC.

The baseline visit will include:

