7. *Cognitive assessment:* NIH Toolbox will be used to assess the following cognitive domains: memory, executive function, language, reading, vocabulary, and processing speed.²

12-week evaluation: All participants will return to complete all in-person evaluations identical to the baseline evaluation in addition to completing acceptability surveys.

MIND+SOUL Single Arm

Education: Participants will receive educational training including ongoing skill building cooking classes (see below), sample weekly menu plans (breakfast, lunch, dinner, snacks), recipe cards (simple recipes), culturally tailored recipe books/handouts, online cooking resources (i.e. preparation videos), grocery shopping guides, faith component (i.e. scripture readings, health devotionals), healthy eating culturally tailored devotional books/handouts (i.e. Healthy Eating, God's Way: Weight Loss Devotional and Challenge: Calm Your Cravings, Overcome Obsessing, Hone Healthy Habits, and Build Biblical Boundaries (Healthy by Design)), affirmations for eating healthy, and a manual that is the basis of the MIND+SOUL diet. The manual includes specific MIND+SOUL diet goals (i.e. specific food group goals).

Skill-Building Health Education/Cooking Classes will be held at the KU ADRC. The group classes will be held once a week for the first 6-weeks of the MIND+SOUL diet intervention. Behavioral strategies shared during the skill-building health education/cooking classes, which are guided by the principles of Capability, Opportunity and Motivation Behavioral Change Model, are designed to provide participants will knowledge and skills (psychological and physical) to improve dietary consumption and adherence to the MIND+SOUL diet.

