Counseling: Counseling: Counseling will consist of one-on-one sessions with a health coach who will provide MIND+SOUL diet continued education and on-going support throughout the diet intervention. This support will consist of education and recommendations specific to the participant's needs, preferences, and local context. The health coach will help participant set dietary goals in relation to the MIND+SOUL diet, help participants develop an action plan for certain situations (i.e. holiday parties, vacations), and provide encouragement in regards to the formation of healthy eating habits. Zoom conference calls will occur bi-weekly for 12-weeks. Each Zoom conference (6 total per participant) is anticipated to last 15-20 minutes each time, with exception to the first Zoom conference call which is anticipated to up to 30 minutes.

Financial support: To improve adherence to the MIND+SOUL diet each participant will receive weekly groceries worth up to \$50 per week (total average of \$600) that will be provided to each participant for 12-weeks. Groceries will be limited to foods within the 10 distinct food groups of the MIND+SOUL diet. These foods will be selected from each week from a community supermarket.

C. Sample size, statistical methods, and power calculation

Single arm: Participants will be in a single arm trial using 3 cohorts (cohort 1 – 10 people, cohort 2 – 10 people, cohort 3 – 10 people). Rationale: Use of a single arm trial will allow for assessment of feasibility and acceptability of the MIND+SOUL diet. Additionally, use of 3 cohort will allow for an opportunity to make revisions between each cohort to further enhance feasibility and acceptability of the MIND+SOUL diet.

Individuals deemed eligible will be placed into 1 of 3 cohort.

Sample Size: A total of 30 participants will be enrolled in the pilot study. Cohort 1 will consist of 10 participants, cohort 2 will consist of 10 people, and cohort 3 will consist of 10 people.

D. Subject Criteria:**1. Inclusion Criteria**

- a. Identify as African American or Black
- b. Age 55 and older
- c. English Speaking
- d. 1 or more of the following CVD risk factors (high blood pressure, high cholesterol, controlled type 2 diabetes overweight/obesity with a BMI of 25 or more as calculated from weight and height at baseline visit)
- e. Cognitively Normal with an AD8 <2 (normal cognition)

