- f. Females of child-bearing potential (i.e., pre-menopausal) must have a negative urine pregnancy test at the screening visit and must agree to use of contraception throughout the trial. The approved methods of contraception are abstinence, the consistent use of an approved oral contraceptive (birth control pill or "the pill"), an intrauterine device (IUD), hormonal implants, contraceptive injection, double barrier method (diaphragm with spermicidal gel or condom with contraceptive foam).

2. Exclusion Criteria

- a. No CVD risk factors
- b. AD8 equal to or greater than 2
- c. Diagnosed with type 1 diabetes
- d. Uncontrolled diabetes type 1 or type 2
- e. Existing diet plan that subject is unable to pause during trial
- f. No internet connection
- g. Uncontrolled hypertension, by history, or as indicated by sitting systolic blood pressure >165 mmHg or diastolic blood pressure >95 mmHg at the baseline visit. If an initial blood pressure reading is higher than this, an additional attempt (at this visit or on another day) could be used before excluding a patient for uncontrolled hypertension
- h. Neurological diseases that impact cognition
- i. Other medical conditions likely to be negatively impacted by a diet change or that could confound the study data (i.e. Celiac Disease, Ulcerative Colitis)
- j. Unable or unwilling to provide written consent
- k. PI determination that study is unsafe or unsuitable for the participant
- l. Active depression as determined by a score of 5 or above on the PHQ9 and deemed to be clinically significant by the medical monitor

3. Withdraw/Termination criteria:

- a. There is no withdraw or termination criteria
- b. Participants are allowed to participate in other observational studies during their enrollment period, but not interventional trials

Total enrollment is anticipated to last between 3-4 months total, with 1-1.5 months of recruitment per cohort.

E. Specific methods and techniques used throughout the study

This study will require two study visits. Outcome data will be collected at baseline and at the 12 week mark (+/- 2 weeks). The total time commitment for visit 1 is 2.5 hours and visit 2 is 2.5 hours.

Visit 1 – Baseline Evaluation

Estimated duration: 2.5 hours

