Body Composition (30 minutes): At baseline and 12 weeks (\pm 2 weeks), dual energy x-ray absorptiometry (GE Lunar iDXA) will be used to determine fat-free mass, fat mass, and percent body fat. DXA uses very low X-ray doses (0.02mREM) to detect changes in body composition on the order of 1.6-3.8%. Body weight, height and waist circumference will be recorded at baseline and at the 12 week mark (\pm 2 weeks). Weight will be obtained using a digital scale (\pm 0.1 kg; Befour Inc model #PS6600, Saukville, WI) and height will be measured using a stadiometer (Model PE-WM-60-84, Perspective Enterprises, Portage, MI). Body mass index (kg/m²) will be calculated. Waist circumference will be obtained using a calibrated tape.²¹

Dietary Screener Questionnaire (30 minutes): Nutritional health status change will be measured using the NHANES Dietary Screener Questionnaire administered by study personnel.

Skin Carotenoid Content (10 minutes): is a validated, biomarker of fruit and vegetable intake.²⁴⁻²⁶ The "Veggie meter" (Longevity Link Corporation) uses Resonance Raman spectroscopy to non-invasively measure skin carotenoid content. Three measurements will be taken on the fingertip and averaged (total time ~1 minute) by study personnel.

Cognition (30 minutes): Participants will complete a cognitive measurement session at the KU ADRC at the baseline and at the 12-week mark. The NIH Toolbox to assess the following domains: memory, language, reading, vocabulary, processing speed, and executive function.² Specifically the following tests will be administered: NIH-TB List Sorting Working Memory Test, NIH-TB Picture Vocabulary Test,

NIH-TB Oral Reading Recognition Test, and the NIH-TB Pattern Comparison Processing Speed Test, and NIH-TB Flanker Inhibitory Control and Attention. Test will be administered by a psychometrician.

Visit 2 – 12-week Evaluation

Estimated duration: 2.5 hours

At 12 weeks (\pm 2 weeks), participants will return to complete blood draw, blood pressure, DXA scan for body composition, height, weight, waist circumference, dietary screener questionnaire, skin carotenoid assessment, cognitive testing, a check for adverse events, and survey completion (acceptability surveys).

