REDCap is a secure, web-based application designed to support data capture for research studies, providing: 1) an intuitive interface for validated data entry; 2) audit trails for tracking data manipulation and export procedures; 3) automated export procedures for seamless data downloads to common statistical packages; and 4) procedures for importing data from external sources. REDCap on the KUMC campus sits on a HIPAA compliant, password protected server. The KU ADRC has extensive experience building and maintaining REDCap databases, including those used for the preliminary data in this application. Confidentiality is strictly safeguarded by HIPAA-compliant standards.

- E. Quality Assurance / Monitoring:** The study team will perform source data verification and self-assessment of records at the completion of each cohort of the intervention to ensure that data are accurate.

V. Data Analysis and Reporting

- A. Statistical and Data Analysis:** Information from these tests will be entered into a research database. The PI, SC, and study team will supervise the data acquisition. Data will be coded for confidentiality and only the PI, SC, study team and statistician will have access to the code. Hard copies of study files are kept in a dedicated, locked cabinet in a badge-access area. Subject data will be coded prior to sending it to the statistician for statistical analyses.

Using an ANOVA model, 10 samples per time point (total 3 time points) will achieve 80% of power to detect a maximum change of the standardized measurement (raw measurement divided by its standard deviation) across the 3 time points with a magnitude 1.3 (A

magnitude <1 will mean the change is less than the noise level. I would consider a magnitude of 1.3 a subtle or a medium sized change.).

Focus group data will be analyzed using the constant comparative coding analysis.²⁷ Specifically, we will assess if the emerged themes were consistent across the two groups. The analysis will occur in three stages.²⁸ During the first stage of open coding, data will be placed into small units and will be coded for each unit. Axial coding will occur during the second stage in which the codes will be grouped into categories. Selective coding will occur during the third stage in which the PI will construct themes that express the content of each of the identified grouped categories.

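### The only power statement (ANOVA, 10 samples at each of 3 time points, 80% power for 1.3 SD) does not describe this trial, which measures one arm of 30 at two time points

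*Combined protocol and SAP*

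**What the plan says.** Section V.A gives power for an ANOVA: "10 samples per time point (total 3 time points) will achieve 80% of power to detect a maximum change of the standardized measurement", the magnitude being 1.3 on a scale where the raw measurement is divided by its standard deviation. Alpha, the outcome, the pattern of the three means, the within-person correlation and any allowance for missing data are not given.

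The design is different elsewhere:

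- **Visits.** Section II.E says "This study will require two study visits" and places the outcome measurements at baseline and week 12. For cognition it says "Participants will complete a cognitive measurement session at the KU ADRC at the baseline and at the 12-week mark". Section II.B describes the second visit: "All participants will return to complete all in-person evaluations identical to the baseline evaluation in addition to completing acceptability surveys". The schedule table in II.E has no third column for any quantitative outcome.
- **Sample.** Section II.C says "A total of 30 participants will be enrolled in the pilot study", in one arm, as three successive cohorts of 10.
- **Power.** The heading of II.C promises a power calculation, but the section contains none. Under Secondary Outcomes, section I.A mentions power only for a future randomised trial.
- **Analysis.** Aim 2 in section I.A concerns change in cognition in a single arm, yet it assigns an ANOVA of differences between groups. No groups are defined.

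**The concern.** A power statement should describe the comparison that the trial will make. This one has a third time point that is never scheduled and 10 observations per time point where up to 30 are planned. The focus groups after cohorts 1 and 2 do not supply the missing time point, because they are qualitative and involve a few participants.

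The protocol therefore does not say what baseline-to-week-12 change its secondary outcomes can detect, although those outcomes are meant to inform the power and sample size of a later randomised trial. The ANOVA sentence under Aim 2 adds to the problem. If its groups are the three cohorts, it compares cohorts with one another and does not test change within participants, which is the Aim 2 question.

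**Working it through.** **Inputs from the plan:** 10 per time point, 3 time points, 80% power and 1.3 raw SD (V.A); 30 participants in three cohorts of 10 (II.C); two outcome visits (II.E). **Assumed, because the plan gives none:** two-sided 5% level and within-person correlations ρ from 0 to 0.8. The 24-pair case (0.8 × 30) only illustrates missing data.

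**1. The plan's own figure.** For a one-way ANOVA with three levels of 10 (df 2, 27), λ = 10 × Σ(μᵢ − μ̄)².

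- Means 0, 0.65, 1.3: λ = 10 × 2 × 0.65² = 8.45, power 69.1%.
- Means 0, 0, 1.3: λ = 10 × 1.3² × 2/3 = 11.27, power 81.8%.

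A repeated-measures ANOVA on 10 people (df 2, 18) uses λ/(1 − ρ).

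- Even spacing: 76.6%, 79.9% and 82.2% at ρ = 0.2, 0.26 and 0.3.
- Means 0, 0, 1.3: 79.4% at ρ = 0.

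So 80% is attainable for that model, depending on inputs the plan does not state.

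**2. The scheduled comparison, baseline against week 12.** A paired t test has noncentrality dz√n on n − 1 df, where dz is the mean change divided by the SD of the change score. In raw SD units the detectable change is dz × √(2(1 − ρ)). At 80% power:

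| Pairs | dz | ρ=0 | ρ=0.3 | ρ=0.5 | ρ=0.7 | ρ=0.8 |
|---|---|---|---|---|---|---|
| 30 (pooled) | 0.53 | 0.75 | 0.63 | 0.53 | 0.41 | 0.33 |
| 24 (illustration) | 0.60 | 0.84 | 0.71 | 0.60 | 0.46 | 0.38 |
| 10 (one cohort) | 1.00 | 1.41 | 1.18 | 1.00 | 0.77 | 0.63 |

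Adding a cohort term to the pooled analysis (27 error df) leaves dz at 0.53.

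**3. Power at the stated 1.3 raw SD.** At ρ = 0, dz = 1.3/√2 = 0.919.

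- 30 pairs: noncentrality 0.919 × √30 = 5.03, power 99.8%, and higher at larger ρ.
- 10 pairs: noncentrality 0.919 × √10 = 2.91, power 73.5%. It reaches 80% where 1.3 = 0.996 × √(2(1 − ρ)), which gives ρ = 1 − (1.3/0.996)²/2 = 0.148.

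**4. If the time points were meant as cohorts.** A one-way ANOVA of change scores, 3 × 10, has 80% power when the largest difference between cohorts is 1.27 SD of the change score (means 0, 0, d) or 1.47 (means 0, d/2, d). If every cohort improves equally, λ = 0 and the test rejects only at its 5% error rate, however large the improvement. A simulation with a change of 1 SD in every cohort gave 5.1% in 20,000 runs.

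**The case against.** The strongest reply is that time point is a slip for cohort. Cohorts run in sequence, there are three of 10, and II.C says that "use of 3 cohort will allow for an opportunity to make revisions between each cohort". Section I.A also refers to an ANOVA between groups. On that reading the 1.3 lies inside the 1.27 to 1.47 range found in step 4, so the figure roughly fits an analysis the trial could run. This is a plausible origin for the numbers. It does not rescue the statement: the text says time points, and a comparison of cohorts does not address change from baseline to week 12.

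The second reply is that little depends on the error. With cohorts pooled, the statement is conservative at every non-negative correlation. The unfavourable case needs each cohort analysed alone, which the plan does not propose, and a correlation below about 0.15; even at zero, power falls only from 80% to 73.5%. The sample of 30 is not derived from the power sentence, and the future trial will use the observed data. All of this stands, and it limits the importance of the point. It does not make the statement describe this trial.

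It is also fair that the undefined groups under Aim 2 are a separate defect of specification. It is treated here because the same decision about cohorts settles both.

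**Conclusion.** The concern holds. The stated 80% power for 1.3 SD does not apply to the baseline-to-week-12 comparison, and no other power statement exists. The arithmetic of the statement is not shown to be wrong.

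The direction of the mismatch depends on a choice the protocol does not make. With cohorts pooled, the detectable change is 0.53 SD of the change score, so 1.3 raw SD is far larger than needed. With cohorts analysed singly it is 1.00 SD of the change score. These figures rest on a two-sided 5% level, 80% power, complete pairs and assumed correlations.

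Underpowering is not shown, and the primary outcomes are untouched. The statement should still be corrected, because it is wrong as written and cheap to put right.

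**What to change.** **Section V.A.** Remove the reference to three time points and replace the power sentence with a paired, two-visit statement that gives alpha, correlation and the pooling assumption. One option:

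*With 30 paired measurements, pooling the three cohorts, a two-sided 5% paired t test has 80% power to detect a mean baseline-to-week-12 change of 0.53 SD of the change score (0.75, 0.53, 0.41 and 0.33 raw SD at assumed within-person correlations of 0, 0.5, 0.7 and 0.8); with 24 pairs, 0.60 SD of the change score.*

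State that pooling assumes similar change across cohorts although the intervention may be revised between them. If cohorts will be analysed separately, say so and give the 10-pair figure of 1.00 SD of the change score instead.

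**Section I.A, Aim 2.** Define the groups or replace the sentence. One option:

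*Change from baseline to week 12 will be analysed within participants (paired t test or the equivalent two-time-point repeated-measures ANOVA) and reported as mean change with 95% CI.*

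If a comparison between cohorts is also intended, keep it as a separate analysis labelled exploratory.

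**Cost.** Text changes in two places and one sponsor decision: whether cohorts are pooled and whether they are to be compared. No added participants, visits or procedures.
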